## 12.2.3 Methods for Evaluation of Measurable Disease

All measurements should be taken and recorded in metric notation using a ruler or calipers.

The same method of assessment and the same technique should be used to characterize each identified and reported lesion at baseline and during follow-up.

Imaging-based evaluation is preferred to evaluation by clinical examination unless the lesion(s) being followed cannot be imaged but are assessable by clinical exam.

- 12.2.3.1 Clinical lesions: Clinical lesions will only be considered measurable when they are superficial (e.g., skin nodules and palpable lymph nodes) and  $\geq 10$  mm diameter as assessed using calipers (e.g., skin nodules). In the case of skin lesions, documentation by color photography, including a ruler to estimate the size of the lesion, is recommended.
- 12.2.3.2 Chest x-ray: Lesions on chest x-ray are acceptable as measurable lesions when they are clearly defined and surrounded by aerated lung. However, CT is preferable.
- 12.2.3.3 Conventional CT and MRI: This guideline has defined measurability of lesions on CT scan based on the assumption that CT slice thickness is 5 mm or less. If CT scans have slice thickness greater than 5 mm, the minimum size for a measurable lesion should be twice the slice thickness. MRI is also acceptable in certain situations (e.g. for body scans). Ideally, the same type of scanner should be used and the image acquisition protocol should be followed as closely as possible to prior scans.
- 12.2.3.4 PET-CT: At present, the low dose or attenuation correction CT portion of a combined PET-CT is not always of optimal diagnostic CT quality for use with RECIST measurements. However, if the site can document that the CT performed as part of a PET-CT is of identical diagnostic quality to a diagnostic CT (with IV and oral contrast), then the CT portion of the PET-CT can be used for RECIST measurements and can be used interchangeably with conventional CT in accurately measuring cancer lesions over time. Note, however, that the PET portion of the CT introduces additional data which may bias an investigator if it is not routinely or serially performed.
- 12.2.3.5 Tumor markers: Tumor markers alone cannot be used to assess response. If markers are initially above the upper normal limit, they must normalize for a patient to be considered in complete clinical response.
- 12.2.3.6 Cytology, Histology: These techniques can be used to differentiate between partial responses (PR) and complete responses (CR) in rare cases (e.g., residual lesions in tumor types, such as germ cell tumors, where known residual benign tumors can remain).

Cytology should be obtained if an effusion appears or worsens during treatment when the measurable tumor has met criteria for response or stable disease.

12.2.3.7 FDG-PET: While FDG-PET response assessments need additional study, it is sometimes reasonable to incorporate the use of FDG-PET scanning to complement CT scanning in assessment of progression (particularly possible 'new' disease). New lesions on the basis of FDG-PET imaging can be identified according to the following algorithm:

Institute of the National Institutes of Health

CHILDREN'S

ONCOLOGY

GROUP

THIS PROTOCOL IS FOR RESEARCH PURPOSES ONLY, SEE PAGE 1 FOR USAGE POLICY

- a. Negative FDG-PET at baseline, with a positive FDG-PET at followup is a sign of PD based on a new lesion.
- b. No FDG-PET at baseline and a positive FDG-PET at follow-up: If the positive FDG-PET at follow-up corresponds to a new site of disease confirmed by CT, this is PD. If the positive FDG-PET at follow-up is not confirmed as a new site of disease on CT, additional follow-up CT scans are needed to determine if there is truly progression occurring at that site (if so, the date of PD will be the date of the initial abnormal FDG-PET scan). If the positive FDG-PET at follow-up corresponds to a pre-existing site of disease on CT that is not progressing on the basis of the anatomic images, this is not PD.
- Note: A 'positive' FDG-PET scan lesion means one that is FDG avid with an uptake greater than twice that of the surrounding tissue on the attenuation corrected image.

# 12.2.4 Response Criteria for Patients with Solid Tumor and Measurable Disease

# 12.2.4.1 Evaluation of Target Lesions

Complete Response (CR) :	Disappearance of all target and non-target lesions. Any pathological lymph nodes (whether target or non-target) must have reduction in short axis to <10 mm. If immunocytology is available, no disease must be detected by that methodology. Normalization of urinary catecholamines or other tumor markers if elevated at study enrollment (for patients with neuroblastoma).
Partial Response (PR):	At least a 30% decrease in the sum of the diameters of target lesions, taking as reference the baseline sum diameters
Progressive Disease (PD) :	At least a 20% increase in the sum of the diameters of target lesions, taking as reference the smallest sum on study (this includes the baseline sum if that is the smallest on study). In addition to the relative increase of 20%, the sum must also demonstrate an absolute increase of at least 5 mm. (Note: the appearance of one or more new lesions is also considered progressions). Note: in presence of SD or PR in target disease but unequivocal progression in non-target or non-measurable disease, the patient has PD if there is an overall level of substantial worsening in non-target disease such that the overall tumor burden has increased sufficiently to merit discontinuation of therapy

Institute of the National Institutes of Health

Stable Disease (SD):

Neither sufficient shrinkage to qualify for PR nor sufficient increase to qualify for PD, taking as reference the smallest sum diameters while on study

#### 12.2.4.2 Evaluation of Non-Target Lesions

Complete Response (CR): Disappearance of all non-target lesions and normalization of tumor marker level. All lymph nodes must be non-pathological in size (<10 mm short axis)

Note: If tumor markers are initially above the upper normal limit, they must normalize for a patient to be considered in complete clinical response.

- Non-CR/Non-PD: Persistence of one or more non-target lesion(s) and/or maintenance of tumor marker level above the normal limits
- Progressive Disease (PD): Appearance of one or more new lesions and/or *unequivocal progression* of existing non-target lesions. *Unequivocal progression* should not normally trump target lesion status. It must be representative of overall disease status change, not a single lesion increase.

## 12.2.5 Overall Response Assessment

Table 1:	For Patients with Measurable Disease	(i.e., Target Disease)

Target Lesions	Non-Target Lesions	New Lesions	Overall Response	Best Overall Response when Confirmation is
CD	CD	NT	CD	Required*
CR	CR	No	CR	$\geq$ 28 days Confirmation
CR	Non-	No	PR	
	CR/Non-PD			$\geq$ 28 days Confirmation
CR	Not evaluated	No	PR	
PR	Non-	No	PR	
	CR/Non-			
	PD/not			
	evaluated			
SD	Non-	No	SD	documented at least once $\geq$
	CR/Non-			28 days from baseline
	PD/not			-
	evaluated			
PD	Any	Yes or No	PD	
Any	PD**	Yes or No	PD	no prior SD, PR or CR
Any	Any	Yes	PD	
* See REC	IST 1.1 manuscript	for further deta	ails on what is	evidence of a new lesion.

\*\* In exceptional circumstances, unequivocal progression in non-target lesions may be accepted as disease progression.

Note: Patients with a global deterioration of health status requiring discontinuation of treatment without objective evidence of disease progression at that time should be reported as "*symptomatic deterioration*." Every effort should be made to document the objective progression even after discontinuation of treatment.

Table 2: For Patients with Non-Measurable Disease (i.e., Non-Target Disease)

Non-Target Lesions	New Lesions	Overall Response
CR	No	CR
Non-CR/non-PD	No	Non-CR/non-PD*
Not all evaluated	No	not evaluated
Unequivocal PD	Yes or No	PD
Any	Yes	PD

\* 'Non-CR/non-PD' is preferred over 'stable disease' for non-target disease since SD is increasingly used as an endpoint for assessment of efficacy in some trials so to assign this category when no lesions can be measured is not advised

CT/MRI	MIBG	Bone Scan	Bone Marrow	Catechol	Overall
PD	Any	Any	Any	Any	PD
Any	PD	Any	Any	Any	PD
Any	Any	PD	Any	Any	PD
Any	Any	Any	PD	Any	PD
SD	CR/PR/SD	Non-PD	Non-PD	Any	SD
PR	CR/PR	Non-PD	Non-PD	Any	PR
CR/PR	PR	Non-PD	Non-PD	Any	PR
CR	CR	Non-PD	Non-PD	Elevated	PR
CR	CR	CR	CR	Normal	CR

#### 12.2.6 Overall Best Response Assessment

Each patient will be classified according to his "best response" for the purposes of analysis of treatment effect. Best response is determined as outlined in Section 12.7 from a sequence of overall response assessments.

#### 12.3 **Response Criteria for Patients with Solid Tumors and Evaluable Disease**

#### 12.3.1 Evaluable Disease

The presence of at least one lesion, with no lesion that can be accurately measured in at least one dimension. Such lesions may be evaluable by nuclear medicine techniques, immunocytochemistry techniques, tumor markers or other reliable measures.

# 12.3.2 Complete Response

Disappearance of all evaluable disease.

#### 12.3.3 Partial response

Partial responses cannot be determined in patients with evaluable disease

Institute of the National Institutes of Health

12.3.4 Stable Disease (SD)

That which does not qualify as Complete Response (CR), Partial Response (PR), or Progressive Disease.

12.3.5 Progressive Disease

The appearance of one or more new lesions or evidence of laboratory, clinical, or radiographic progression.

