#### medical or research record which will serve as the source document for verification at the time of audit.

#### 4.1 **Inclusion** Criteria

- 4.1.1 Age: Patients must be > than 12 months and  $\leq 21$  years of age at the time of study enrollment.
- 4.1.2 Diagnosis: Patients with recurrent or refractory solid tumors, including CNS tumors, are eligible. Patients must have had histologic verification of malignancy at original diagnosis or relapse except in patients with intrinsic brain stem tumors, optic pathway gliomas, or in patients with pineal tumors and elevations of CSF or serum tumor markers including alpha-fetoprotein or beta-HCG.
- 4.1.3 Disease Status: Patients must have either measurable or evaluable disease (see Sections 12.2 and 12.3 for definitions).
- 4.1.4 Therapeutic Options: Patient's current disease state must be one for which there is no known curative therapy or therapy proven to prolong survival with an acceptable quality of life.
- Performance Level: Karnofsky  $\geq$  50% for patients > 16 years of age and Lansky  $\geq$ 4.1.5 50 for patients  $\leq$  16 years of age (See Appendix I). Note: Neurologic deficits in patients with CNS tumors must have been relatively stable for at least 7 days prior to study enrollment. Patients who are unable to walk because of paralysis, but who are up in a wheelchair, will be considered ambulatory for the purpose of assessing the performance score.

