## 11.5 Pharmacokinetic and Correlative Studies and Response Analysis

A descriptive analysis of pharmacokinetic (PK) parameters of LY2606368 will be performed to define systemic exposure, drug clearance, and other pharmacokinetic parameters. The PK parameters will be summarized with simple summary statistics, including means, medians, ranges, and standard deviations (if numbers and distribution permit).

While the primary aim of this study is to evaluate the toxicity of LY2606368, patients will have disease evaluations performed as indicated in Section 8.1. Disease response will be assessed according to RECIST criteria for patients with solid tumors, and will be reported descriptively.

All these analyses will be descriptive and exploratory and hypotheses generating in nature.

<sup>1These distributions are based on historical Phase 1 enrollments.

```
NCI Pediatric Early Phase
Clinical Trials Network
```

A program funded by the National Cancer

This protocol is for research purposes only, see page 1 for usage policy

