# 12.2.1 Definitions

- 12.2.1.1 Evaluable for objective response: Patients who exhibit objective disease progression prior to the end of cycle 1 will be considered evaluable for response. For all other patients, only those patients who have measurable disease present at baseline, have received at least one cycle of therapy, and have had their disease re-evaluated will be considered evaluable for response.
- 12.2.1.2 Evaluable Non-Target Disease Response: Patients who have lesions present at baseline that are evaluable but do not meet the definitions of measurable disease, have received at least one cycle of therapy, and have had their disease re-evaluated will be considered evaluable for non-target disease. The response assessment is based on the presence, absence, or unequivocal progression of the lesions.

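### Solid-tumour patients with imaging-visible but non-measurable disease fall under two response rules that differ on progressive and stable disease, and nothing says which governs

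*Combined protocol and SAP*

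**What the plan says.** Eligibility Section 4.1.3 admits patients without measurable disease: "Patients must have either measurable or evaluable disease (see Sections 12.2 and 12.3 for definitions".

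Section 12.2 reaches these patients. Section 12.2.1.2 covers baseline lesions that are evaluable without being measurable, and states: "The response assessment is based on the presence, absence, or unequivocal progression of the lesions". Section 12.2.5 gives them their own overall-response table (Table 2), in which PD follows from a new lesion or unequivocal progression and the middle category is Non-CR/non-PD. Its footnote prefers that label to stable disease "for non-target disease since SD is increasingly used as an endpoint for assessment of efficacy in some trials" and advises against SD when nothing can be measured.

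Section 12.3 also reaches them. It applies when there is at least one lesion and none that can be accurately measured. Section 12.3.5 defines PD as "The appearance of one or more new lesions or evidence of laboratory, clinical, or radiographic progression". Section 12.3.4 defines SD as the remainder: "That which does not qualify as Complete Response (CR), Partial Response (PR), or Progressive Disease".

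Sections 12.2.6 and 12.3.6 both send the result to Section 12.7, where Table 3 derives best response from Progression, Stable, PR and CR. On analysis, Section 11.5 says: "Disease response will be assessed according to RECIST criteria for patients with solid tumors, and will be reported descriptively".

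**The concern.** A patient with only bone lesions, which Section 12.2.2.3 lists as non-measurable, meets both definitions. The two sections then disagree on what counts as progression and on what to call disease that has not changed.

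Antitumour activity is secondary aim 1.2.1 and is only described, so the category counts are the result; no model or test stands behind them. If two sites, or a site and the statistics office, apply different sections, the SD and PD counts mix two definitions and cannot be interpreted without knowing which was used for whom. The label also has consequences elsewhere: Section 8.2 sends SD lasting at least 6 cycles to central review, Section 5.2 makes the next cycle conditional on at least stable disease, and Section 10.1a makes PD a ground for removal from protocol therapy.

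**Working it through.** The plan states no figure on this point, so the check sets the texts side by side.

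**Step 1: do the populations overlap?** Section 12.2.1.2 needs lesions that are evaluable but not measurable. Section 12.3.1 needs at least one lesion and none accurately measurable. Bone-only disease satisfies both.

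**Step 2: is there a precedence rule?** Sections 4.1.3, 5.2, 8.1, 10.1, 11.5 and 12.7 were read for one. None assigns these patients to one section for response classification.

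**Step 3: classify the same patient under each rule.**

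| Finding at an assessment | 12.2.1.2 and Table 2 | 12.3 |
|---|---|---|
| New lesion | PD | PD |
| All lesions gone, markers normal | CR | CR |
| Lesions unchanged, no other worsening | Non-CR/non-PD; SD advised against | SD (12.3.4) |
| Lesions unchanged, marker or clinical status worse | Non-CR/non-PD | PD (12.3.5) |

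The rules agree in the first two rows and differ in the last two. For clinical decline there is a further contrast: a note in Section 12.2.5 has global deterioration without objective progression reported as symptomatic deterioration, whereas 12.3.5 counts clinical progression as PD.

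**Step 4: carry the result into Table 3.** Take two consecutive assessments of a bone-only patient.

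- Unchanged, then unchanged. Under 12.3: Stable, Stable, so best response is Stable. Under Table 2: Non-CR/non-PD twice, for which Table 3 has no row.
- Unchanged, then unchanged lesions with a rising marker. Under 12.3: Stable, Progression, so best response is Progressive disease. Under Table 2: Non-CR/non-PD twice, again with no row.

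**Step 5: trace the label to other sections.**

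- 8.2: unchanged disease for 6 or more cycles triggers central review if called SD. Read literally, it does not if called Non-CR/non-PD.
- 5.2: the continuation condition is written in terms of SD, a label Table 2 avoids.
- 10.1a: removal for PD accepts clinical evidence, including serum markers, but refers to Section 12.0 as a whole, which contains both rules.
- 8.1 footnote 5: for solid tumours, progression determined on clinical or laboratory evidence need not be confirmed radiographically.

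**The case against.** **Routing can be inferred.** Section 4.1.3 can be read respectively, with 12.2 for measurable and 12.3 for evaluable disease, and 12.3 carries evaluable disease in its title. Section 8.1 footnote 5 and Section 10.1a also lean towards 12.3.5. This is a fair reading, but it does not settle the matter. Section 4.1.3 points to definitions of disease, not to response rules. On that reading 12.2.1.2 and Table 2, written for non-measurable disease, would have almost nobody to apply to. Footnote 5 and 10.1a concern confirmation of progression and removal from therapy. Section 11.5, by naming RECIST, leans the other way, yet does not exclude 12.3, whose results also feed Section 12.7.

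**The SD conflict is mainly one of label.** This largely stands: the Table 2 footnote is advice, and the patient's state is the same. The label still matters because Table 3 has no place for one of the two, and 5.2 and 8.2 are written in terms of the other.

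**A stronger reading on markers.** A reader might infer that the two sections also contradict each other on marker-only complete response, since 12.3.1 says "Such lesions may be evaluable by nuclear medicine techniques, immunocytochemistry techniques, tumor markers or other reliable measures" while 12.2.3.5 says "Tumor markers alone cannot be used to assess response". The documents do not support this. Item 12.2.3.5 stands under a heading on methods for measurable disease, and 12.2.1.2 and Table 2 are based on lesions, so disease followed only by markers fits 12.3 alone. Nor is bone-only disease CR under one section and unassessable under the other: both allow CR. The marker-normalisation condition for CR in 12.2.4.2 also sits under a measurable-disease heading.

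**Response is secondary and descriptive.** This stands, and it limits the weight of the point.

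**Conclusion.** The conflict is real for one group: solid-tumour patients whose only disease is imaging-visible and non-measurable. For them, PD differs when laboratory or clinical status worsens without unequivocal lesion progression, and the name for unchanged disease differs, with no Table 3 row for one of the names. These are two stated rules giving different answers, not merely missing detail.

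The number of patients affected cannot be derived. The documents give no share of evaluable-only patients. A reader might apply an assumed share to the 36 expected enrolments in Section 11.1, but that total includes a 20% allowance for inevaluable patients and may include CNS tumours and MIBG- or marrow-positive neuroblastoma, which have their own criteria in Sections 12.4 to 12.6. PD also differs only for those who worsen in the particular way described, not for every evaluable-only patient.

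The effect is confined to the SD and PD counts, best response and selection for central review. Section 12.2.1.1 ties evaluability for objective response to measurable disease, apart from progression before the end of cycle 1, so response in patients with measurable disease is not in question. DLT, MTD and sample size do not depend on these categories. The correction is worth making because it is cheap, but it does not threaten the primary aims.

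**What to change.** 1. Reconcile 12.2.1.2 and Table 2 with 12.3, and state which one section governs each evaluable-only patient. This review does not choose the PD rule, because PD leads to removal from therapy through 10.1a.
2. Bring 5.2, 8.1 footnote 5, 8.2 and 10.1a into line with the reconciled terms, so that a patient labelled Non-CR/non-PD has an explicit place in the continuation and central-review wording.
3. Add Non-CR/non-PD to Table 3, both as an assessment and as a best response, and report it separately from SD based on measurements.
4. Report PD resting only on laboratory or clinical evidence as a separate line, so that the summary can be read under either definition.

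The cost is wording in these sections and a slightly lower reported SD count. No additional assessments are needed. Item 4 requires the basis for each PD call to be recorded; the case report forms are a separate packet, so whether they already capture it cannot be seen here.

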12.3.6 Overall Best Response Assessment

Each patient will be classified according to his "best response" for the purposes of analysis of treatment effect. Best response is determined as outlined in Section 12.7 from a sequence of overall response assessments.

# 12.4 Response Criteria for Neuroblastoma Patients with MIBG Positive Lesions

12.4.1 MIBG Positive Lesions

Patients who have a positive MIBG scan at the start of therapy will be evaluable for MIBG response. The use of I for MIBG imaging is recommended for all scans. If the patient has only one MIBG positive lesion and that lesion was radiated, a biopsy must be done at least 28 days after radiation was completed and must show viable neuroblastoma.

12.4.2 The following criteria will be used to report MIBG response by the treating institution:

Complete response:Complete resolution of all MIBG positive lesionsPartial Response:Resolution of at least one MIBG positive lesion, with
persistence of other MIBG positive lesionsStable disease:No change in MIBG scan in number of positive lesionsProgressive disease:Development of new MIBG positive lesions

- 12.4.3 The response of MIBG lesions will be assessed on central review using the Curie scale14 as outlined below. Central review responses will be used to assess efficacy for study endpoint. See Section 8.2 for details on transferring images to the Imaging Research Center.
  - NOTE: This scoring should also be done by the treating institution for end of course response assessments.

The body is divided into 9 anatomic sectors for osteomedullary lesions, with a 10th general sector allocated for any extra-osseous lesion visible on MIBG scan. In each region, the lesions are scored as follows. The **absolute extension score** is graded as:

- 0 = no site per segment,
- 1 = 1 site per segment,
- 2 = more than one site per segment,
- 3 = massive involvement (>50% of the segment).

[figure not shown]
The **absolute score** is obtained by adding the score of all the segments. See diagram of sectors below:

[figure not shown]

CHILDREN'S Pediatric Early Phase Clinical Trials Networl NCI ONCOLOGY

GROUP

A program funded by the National Cancer nstitute of the National Institutes of Health

The relative score is calculated by dividing the absolute score at each time point by the corresponding pre-treatment absolute score. The relative score of each patient is calculated at each response assessment compared to baseline and classified as below:

- 1. Complete response: all areas of uptake on MIBG scan completely resolved. If morphological evidence of tumor cells in bone marrow biopsy or aspiration is present at enrollment, no tumor cells can be detected by routine morphology on two subsequent bilateral bone marrow aspirates and biopsies done at least 21 days apart to be considered a Complete Response.
- 2. **Partial response**: Relative score  $\leq 0.2$  (lesions almost disappeared) to  $\leq 0.5$ (lesions strongly reduced).
- 3. Stable disease: Relative score > 0.5 (lesions weakly but significantly reduced) to 1.0 (lesions not reduced).
- 4. Progressive disease: New lesions on MIBG scan.

